- [Table 3-1](#) Objectives and endpoint: Updated to include PDR001 plasma concentrations and PK parameters as a secondary objective for the Japanese safety run-in part of the study.
- [Section 4.1](#) Description of study design: Updated to clarify that Part 3 will be opened in parallel with Part 1 and will assess TNBC patients with a known PD-L1 SP-142 status of IC=0 (<1 %) using the FCT formulation of NIR178. Additionally, explanation was added that Part 3 will explore the safety and pharmacokinetics of the FCT formulation of NIR178.
- [Figure 4-1](#) Study design: Added TNBC with PD-L1 SP142 status of IC=0 (<1 %) as one of the selected tumor groups of Part 3. Additionally, updated Part 3 study design and included language for NIR178 240mg in combination with PDR001 in the Japanese safety run-in.
- [Figure 4-2](#) Study Design Japanese run-in part: Updated figure to reflect current Japanese safety run-in design
- [Section 4.1.3](#) Part 3: NIR178+PDR001 additional exploration in selected tumor types: Updated to clarify that one of the tumor groups selected for Part 3 will include TNBC. Additionally, dose increment criteria for Part 3 was added.
- [Section 4.1.4](#) Japanese safety run-in part: Revised language to state that as of Amendment 6 patients enrolled in the Japanese safety run-in will receive NIR178 240mg BID in combination with PDR001. Additional updates include adding the 240mg dose level to the DLT period language.
- [Section 4.3](#) Definition of end of study: Added language for post-trial access programs or roll over protocols which would allow all ongoing patients to transfer to that clinical study as applicable.
- [Section 5.2](#) Inclusion criteria: Added TNBC with PD-L1 status of IC=0 (<1%) as determined by Ventana PD-L1 SP-142 assay as one of the selected tumor groups of Part 3. Additionally, inclusion criteria for Part 3 TNBC tumor group has been added.
- [Section 5.3](#) Exclusion criteria: Added reference to [Appendix 6](#) which contains the Cockcroft-Gault formula.
- [Section 6.1](#) Study treatment: Updated to note the formulation for Part 3 as NIR178 FCT.
- [Table 6-1](#) Dose and Treatment schedule: Table updated to include a new row for the NIR178 FCT formulation.

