- [Section 6.1.1](#) Dosing Regimen: Updated to change the formulation of NIR178 to FCT in Part 3 of the study and clarified that as of Amendment 6, Japanese safety run-in patients will enroll in NIR178 240mg in combination with PDR001. Additional updates include adding language around dose escalation to NIR178 240mg BID FCT.

- [Table 6-2](#) Criteria for dose reduction/interruption and re-initiation of NIR178 and PDR001 treatment for adverse drug reactions: Revised to include recommended dose modifications for DILI. Additional updates for pneumonitis section include recommending to seek consultation with pulmonologist and managing toxicity per institutional practice. Additionally, updated recommendations were added for AST/ALT elevation management. Guidance provided if suspicion of autoimmune hepatitis due to AST/ALT elevation is noted.
- [Section 6.2.2.1](#) Follow up on potential drug-induced liver injury (DILI) cases: Included additional guidance on DILI follow-up.
- [Table 6-4](#) Clinical and Diagnostic assessments to rule out possible causes of LFT abnormalities: Added table to provide guidance on specific assessments that can be performed in the event of LFT abnormalities.
- [Table 6-5](#) Dose reduction steps for NIR178: Additional table added to note dose reduction steps for patients receiving NIR178 FCT in Part 3 of the study. Additionally, the dose reduction table for NIR178 160mg BID was removed as dose reduction steps are outlined in the NIR178 capsule formulation (hard gelatin capsule) respective table.
- [Section 6.3.2](#) Permitted concomitant therapy requiring caution and/or action: Added language that BCRP substrates in combination with NIR178 should be used with caution.
- [Section 7.1](#) Study flow and visit schedule: Clarified that Part 3 will follow the continuous BID visit schedule. Additional clarification was added that allows the implementation of alternative care if the COVID-19 pandemic limits or prevents on-site study visits.
- [Table 7-1](#): Visit evaluation schedule for patients in Part 1, Part 2 NIR178 S1 (NIR178 Schedule 1-BID continuous dosing), Part 3 and Japanese safety run-in: Added row to note that baseline tumor molecular characteristics for patients will be collected at screening.
- [Section 7.1.1.3](#) Patient demographics and other baseline characteristics: Added clarification that baseline tumor molecular characteristics may be collected to determine eligibility of inclusion in the study.

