4.1.3 Part 3: NIR178+PDR001 additional exploration in selected tumor types

Part 3 of the study will be an expansion of an intermittent or continuous NIR178 dosing schedule (if selected) and further evaluation of safety, efficacy, and immune modulation of the alternate NIR178 schedule in combination with PDR001 in one or two tumor groups of 20 patients each. If Part 3 is initiated, a total of 50 patients would be enrolled to this part. The one or two tumor groups in Part 3 will be selected based on the emerging data from Part 1 and Part 2. If one of the tumor groups selected for Part 3 is NSCLC, this group will enroll patients previously exposed to immunotherapy.

Novartis may decide to not open Part 3 for enrollment based on emerging data from Part 1 and Part 2.

As of Protocol Amendment 6, TNBC is one of the selected tumor groups and will enroll patients with a known PD-L1 SP142 status of IC=0 (<1%). Part 3 of the study will evaluate continuous BID NIR178 dosing schedule using the FCT NIR178 formulation. In specific, evaluation of safety, efficacy, and immune modulation of the continuous NIR178 schedule in combination with PDR001 will be performed in the TNBC tumor group which will consist of 20-30 patients. An additional tumor group may be considered for Part 3 which may enroll 20 patients.

Part 3 of the study will start with the FCT formulation of NIR178 at 160mg BID in combination with PDR001 400mg Q4W as a PK/safety run-in part. After the first 10 patients complete at least 1 cycle, a safety analysis will be conducted to decide whether to increase the NIR178 dose

to 240mg BID or complete Part 3 with NIR178 160mg BID. The dose increment criteria is as follows:

- If < 2 patients of the 10 evaluable patients have Grade 3/4 AEs suspected to be related study drug with 1 cycle of study treatment, dose escalate to 240 mg BID and enroll 20 additional patients
- If 2 or 3 patients of the 10 evaluable patients have Grade 3/4 AEs suspected to be related study drug with 1 cycle of study treatment, 10 more patients will be enrolled at 160 mg BID
- If > 3 patients of the 10 evaluable patients have Grade 3/4 AEs suspected to be related study drug with 1 cycle of study treatment, no additional patients will be enrolled and development of the FCT formulation will be reassessed.

Cumulative data (including safety, tolerability, preliminary anti-tumor activity, PK, and PD) will be reviewed on an ongoing basis by Novartis and study investigators via teleconferences.

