6.1.1 Dosing regimen

Treatment cycle is defined as 28 days.

In Part 1 of the study, all patients will receive NIR178 240 mg twice daily continuously and 400 mg of PDR001 administered every 28 days (prior to Amendment 5, all patients were treated with NIR178 160 mg BID).

In Part 2 of the study, all patients will be randomly assigned to one of the three NIR178 dosing schedules in combination with PDR001:

1. NIR178 S1: Patients will take NIR178 160mg twice daily continuously with PDR001 400mg administered once on day 1, every 28 days.
2. NIR178 S2: Patients will take NIR178 160mg twice daily on days 1-14 of a 28 day cycle together with PDR001 400mg administered once on day 1 every 28 days.
3. NIR178 S3: Patients will take NIR178 160mg twice daily on days 1-7 and days 15-21 of a 28 day cycle together with PDR001 400mg administered once on day 1 every 28 days.

In Part 3 of the study, one or two tumor groups may be selected based on emerging data from Part 1 and Part 2.

As of protocol amendment 6, Part 3 will be opened in parallel with Part 1 to further assess TNBC patients with a PD-L1 SP-142 status of IC=0 (<1%) using NIR178 FCT formulation continuous dosing schedule in combination with PDR001. A second tumor group may be considered for Part 3 after completion of Part 1. The first 10 patients enrolled in Part 3 will receive a NIR178 dose of 160 mg BID FCT, and after all patients complete at least 1 cycle of treatment, safety and PK analysis will be performed to decide whether the dose should be increased to NIR178 240 mg BID FCT. If there is unexpected toxicity due to formulation change the dose will not be escalated to NIR178 240mg BID FCT and an additional 10 patients will be enrolled at NIR178 160mg BID FCT. If the NIR178 160mg BID FCT formulation is considered safe, dose escalation to NIR178 240 mg BID FCT will occur and an additional 20 patients will be enrolled.

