6.4.2 Treatment assignment or randomization

Interactive Response Technology (IRT) will be used for treatment assignment, patient allocation and drug supply management for all patients.

In addition, in Part 2, patients will be randomized to one of the 3 treatment arms ([Section 4.1](#) and [Section 6.1](#)) in a ratio of 1:1:1 through IRT.

The randomization numbers will be generated using the following procedure to ensure that treatment assignment is unbiased. A patient randomization list will be produced by the Interactive Response Technology (IRT) provider using a validated system that automates the random assignment of patient numbers to randomization numbers. These randomization numbers are linked to the different treatment arms, which in turn are linked to medication numbers. A separate medication randomization list will be produced by or under the responsibility of Novartis Drug Supply Management using a validated system that automates the random assignment of medication numbers to medication packs containing each of the study treatments.

Prior to dosing, all patients who fulfill all inclusion/exclusion criteria will be randomized via IRT to one of the treatment arms. The investigator or his/her delegate will call or log on to the IRT and confirm that the patient fulfills all the inclusion/exclusion criteria. The IRT will assign a randomization number to the patient, which will be used to link the patient to a treatment arm and will specify a unique medication number for the first package of study treatment to be dispensed to the patient. The randomization number will not be communicated to the caller.

For Japanese safety run-in part: Patients will be assigned by Novartis manually, outside IRT system. IRT will not be used for this part.

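### Protocol 6.1.1 restates the Part 3 dose gate without its stop branch, so it conflicts with 4.1.3 when more than 3 of the first 10 patients have related Grade 3/4 events

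*Protocol*

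**What the plan says.** Protocol 4.1.3 starts Part 3 with 10 patients on 160 mg BID FCT plus PDR001. Once they have completed at least one cycle, it sorts the result by how many of the 10 evaluable patients had Grade 3/4 events suspected to be drug-related in that cycle:

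- fewer than 2: escalate to 240 mg BID and enrol 20 more;
- 2 or 3: enrol 10 more at 160 mg BID;
- more than 3: "no additional patients will be enrolled and development of the FCT formulation will be reassessed".

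SAP 1.1.3 repeats all three branches, and Table 10-6 in Protocol 10.8 is tabulated on the same three tiers.

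Protocol 6.1.1 covers the same 10 patients and the same decision in two sentences. The first reads "If there is unexpected toxicity due to formulation change the dose will not be escalated", and its consequence is that "an additional 10 patients will be enrolled at NIR178 160mg BID FCT". The second reads "If the NIR178 160mg BID FCT formulation is considered safe, dose escalation to NIR178 240 mg BID FCT will occur", with 20 more patients. Section 6.1.1 gives no event count, no toxicity grade, no outcome in which enrolment ends, and no reference to 4.1.3.

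**The concern.** A reader who takes the gate from 6.1.1 finds no toxicity result that ends enrolment. Any toxicity attributed to the formulation, however frequent, leads to 10 more patients at the dose that produced it. Section 4.1.3 enrols nobody in the worst tier. For one possible outcome of a safety gate, the protocol therefore gives two incompatible actions.

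The amendment history does not settle which applies. The Amendment 6 list of changes says of Section 4.1.3 that "dose increment criteria for Part 3 was added" and describes the change to Section 6.1.1 as "adding language around dose escalation to NIR178 240mg BID FCT". Both texts entered together, so neither replaces the other by date.

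The missing branch matters because the gate tests a new formulation. Protocol 2.3 gives the reasons for starting at 160 mg: 240 mg BID is the maximum tolerated dose with the capsule, and the tablet raised bioavailability by 17% in dogs. Protocol 8.6 provides no independent data monitoring committee, so the written rule carries more of the load.

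**Working it through.** **Step 1. The two rules side by side.** Inputs are Protocol 4.1.3, SAP 1.1.3 and Protocol 6.1.1. Totals include the first 10 patients.

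| Patients of 10 with related Grade 3/4 events | 4.1.3 and SAP 1.1.3 | 6.1.1 | Difference |
|---|---|---|---|
| fewer than 2 | 20 more at 240 mg; 10 + 20 = 30 | if judged safe, 20 more at 240 mg; 10 + 20 = 30 | same action, no count in 6.1.1 |
| 2 or 3 | 10 more at 160 mg; 10 + 10 = 20 | if judged unexpectedly toxic, 10 more at 160 mg; 10 + 10 = 20 | same action, no count in 6.1.1 |
| more than 3 | none; 10 + 0 = 10 | 10 more at 160 mg; 10 + 10 = 20 | 10 patients |

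The possible totals are 30, 20 or 10 under 4.1.3, but only 30 or 20 under 6.1.1. Neither branch of 6.1.1 can produce the total of 10, so the last row is a real conflict and not a matter of how the toxicity is labelled.

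**Step 2. Reproduce the plan's figure.** Let X be the number of the 10 patients with an event, binomial with n = 10 and true rate p.

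P(X ≤ 1) = (1 − p)^10 + 10p(1 − p)^9

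At p = 0.09 this is 0.3894 + 0.3851 = 0.7746 (unrounded terms), the 77% stated in Protocol 10.8.

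**Step 3. Probability of the conflicting tier.**

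P(X > 3) = sum over k = 4 to 10 of C(10,k) p^k (1 − p)^(10 − k)

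At p = 0.09 the terms for k = 4, 5 and 6 are 0.0078, 0.0009 and 0.0001, and the total is 0.0088.

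| True rate | P(0 or 1) | Table 10-6 | P(more than 3) | Table 10-6 |
|---|---|---|---|---|
| 5% | 0.9139 | 0.91 | 0.0010 | 0.00 |
| 9% | 0.7746 | 0.77 | 0.0088 | 0.01 |
| 12% | 0.6583 | 0.66 | 0.0239 | 0.02 |
| 15% | 0.5443 | 0.54 | 0.0500 | 0.05 |

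All twelve cells of Table 10-6, including the middle tier not shown here, reproduce to two decimals.

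**Step 4. Beyond the planning rates.** Table 10-6 stops at 15%. At assumed true rates of 20%, 30% and 40%, P(more than 3) is 12.1%, 35.0% and 61.8%. The conflicting tier is rare if the tablet behaves as planned and common if it does not.

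**The case against.** The strongest reply is that the documents show which text governs. Section 4.1.3 holds the named, counted criteria. Protocol 2.3 sends the reader to 4.1.3 for the dose decision, 10.8 refers to 4.1.3 for Part 3 and uses its tiers in Table 10-6, and SAP 1.1.3 repeats the rule in full. On that view 6.1.1 is an incomplete summary of the two branches that continue enrolment, with the correct numbers of 10 and 20. Most of this stands: 4.1.3 is the likely governing text. It does not cure 6.1.1, which tells the reader without qualification to enrol 10 more after unexpected toxicity and does not point to 4.1.3.

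A second reply is that other safeguards exist. The sponsor may terminate for safety (4.4), the study team monitors aggregate safety (8.6), and Table 6-2 governs individual patients. These are general powers. They do not supply the outcome missing from the specific rule.

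A third reply is practical. SAP Section 4 records closure for lack of efficacy, with no Part 3 patients at 240 mg. That stands too: correcting 6.1.1 will not change any patient's enrolment.

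Two stronger readings are tempting, and the documents support neither. A reader might infer that 6.1.1 contradicts the whole gate. It does not: in the two lower tiers its actions can be matched to those of 4.1.3, and what it lacks there is the counts. A reader might also infer that a site could go on enrolling by itself after a toxic result. Cumulative Part 3 data "will be reviewed on an ongoing basis by Novartis and study investigators via teleconferences", and interactive response technology "will be used for treatment assignment, patient allocation and drug supply management for all patients" outside the Japanese run-in. The exposure is an ambiguous sponsor-level decision.

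**Conclusion.** The point holds, limited to the tier with more than 3 of 10. There 4.1.3 and SAP 1.1.3 enrol no further patients, while 6.1.1 as written enrols 10 more at 160 mg BID FCT. The probability of reaching that tier is 0.1% to 5.0% over the protocol's planning rates of 5% to 15%. The calculation assumes independent patients with a common event rate and exactly 10 evaluable patients. The figures above 15% rest on assumed rates that the protocol does not give.

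This is an internal inconsistency in a stated safety rule. It affects no sample-size justification, operating characteristic or primary analysis, and with the study closed it bears on the plan as written. It is still worth correcting, because the section that is wrong is the dosing section and its error falls in the worst safety outcome.

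**What to change.** In Protocol 6.1.1, replace the two sentences on unexpected toxicity and on the tablet being considered safe with the three-branch rule of 4.1.3, including the stop branch. A reference to Section 4.1.3, as Protocol 2.3 already has, would do equally well and leaves only one copy of the rule to maintain.

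The footnotes to Figure 4-1 and Table 6-5 can stay. Their two-way wording echoes the lead-in to 4.1.3 and attaches no enrolment numbers.

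The cost is two sentences in one section. Sample size, tables and analyses do not change.

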6.1.2 Ancillary treatments

Patients should not receive pre-medication to prevent an infusion reaction before the first infusion of study treatment, in order to determine if pre-medication is necessary. If a patient experiences an infusion reaction, he/she may receive pre-medication on subsequent dosing days. The pre-medication should be chosen per institutional standard of care, at the discretion of the treating physician.

Acute allergic reactions should be treated as needed per institutional standard of care. In the event of anaphylactic/anaphylactoid reactions, this includes any therapy necessary to restore normal cardiopulmonary status. If a patient experiences a Grade 3 anaphylactic/anaphylactoid reaction, the patient will be discontinued from the study. The patient may resume study treatment following documented discussion with the Novartis medical monitor. Guidelines on management of infusion reactions are provided in [Table 6-2](#) (Recommended Dose Modifications).

[figure not shown]
The CTCAE category of “Infusion related reaction” should be used to describe study treatment related infusion reactions, unless the investigator considers another category, such as “Allergic reaction,” “Anaphylaxis,” or “Cytokine release syndrome” more appropriate in a specific situation.

6.1.3 Treatment duration

A patient may continue treatment with study treatment until the patient experiences unacceptable toxicity, confirmed disease progression per iRECIST or [Cheson et al \(2014\)](#) for DLBCL patients or as per PCWG3 guidance ([Appendix 5](#)) for mCRPC and/or treatment is discontinued at the discretion of the investigator or the patient. The patients should not be withdrawn from the study due to progressive disease per RECIST v1.1 or [Cheson et al \(2014\)](#) only unless there is evidence suggesting lack of clinical benefit or clinical deterioration. If a patient has clinical or radiological evidence of disease progression but has evidence of clinical benefit and, in the opinion of the investigator, it is in the patient’s best interest to remain on study, then the patient may continue treatment after documented discussion with the Novartis medical monitor. In addition, treatment beyond disease progression should not jeopardize critical interventions to treat/prevent severe complications, or prevent patients from receiving adequate care ([Section 7.1.2](#)).

To account for possible late responses or responses with a prolonged immune-related tumor flare, patients with iRECIST or [Cheson et al \(2014\)](#) progression, ongoing during or at the end of treatment, may restart treatment if they experience a radiographic response following treatment discontinuation in the absence of interval treatment. Retreatment must begin within 4 weeks of the documented response. The schedule will be the same as the schedule being used prior to treatment discontinuation.

Patients who continue treatment beyond initial disease progression will continue all study procedures as outlined in [Section 7](#). In case of clinical deterioration or suspicion of disease progression, a follow-up imaging assessment should be performed promptly rather than waiting for the next scheduled assessment. Patients with evidence of further disease progression on an imaging assessment or who are no longer deriving clinical benefit will be discontinued.

6.2 Dose modifications

6.2.1 Dose modification and dose delay

For patients who do not tolerate the protocol-specified dosing schedule, dose or schedule adjustments are permitted in order to allow the patient to continue the study treatment. The following guidelines need to be applied:

- For clinical management of suspected immune-related events, reference to consensus management guidelines is recommended such as those provided in the National Comprehensive Cancer Network (NCCN) Guidelines for the Management of Immunotherapy-Related Toxicities (available at : nccn.org/professionals/physician_gls/default.aspx#immunotherapy), the American Society for Clinical Oncology clinical practice guideline for Management of Immune-Related Adverse Events in Patients Treated With Immune Checkpoint Inhibitor Therapy (Brahmer et al 2018) or the European Society for Medical Oncology (ESMO) Clinical Practice Guidelines for Management of Toxicities from Immunotherapy (Haanen et al 2017). Note that in general, study treatment should be interrupted for grade 3 and 4 toxicities and for a subset of lower grade toxicities.
- Consider early referral to specialists with expertise in the diagnosis and management of immune-related AEs to thoroughly investigate events of uncertain etiology
- Events not included in the study protocol or the reference guidance documents should be managed per institutional preference

NIR178 dose may be interrupted and/or reduced for treatment related adverse events during the course of treatment. For NIR178, dose reduction steps should follow guidelines outlined in [Table 6-5](#). Dose reductions are not permitted for PDR001. PDR001 may be delayed due to toxicities. A patient must discontinue treatment with NIR178 and PDR001 if the toxicity recurs with the same or worse severity after treatment is resumed at a lower dose. **For Japanese safety run-in, dose reductions for NIR178 will not be allowed in the DLT observation period.**

Dose modifications/delays of NIR178 and PDR001 for specific adverse events are summarized in [Table 6-2](#). Deviations to mandatory dose interruptions and/or reductions are not allowed. Permanent treatment discontinuation is mandatory for specific events and/or dose interruption periods as indicated in [Table 6-2](#). However, in cases where a patient meeting criteria for permanent discontinuation due to a study treatment-related toxicity is experiencing clinical benefit and, in the opinion of the investigator it is in the patient's best interest to remain on study, the patient may continue treatment after documented discussion with Novartis. All dose interruptions/reductions of NIR178 and dose delays of PDR001 must be recorded on the Dosage Administration Record CRF.

PDR001 and NIR178 dosing may resume once the adverse event has resolved to the specified grade or better (as outlined in [Table 6-2](#)) or baseline. Patients unable to resume combination therapy after resolution of an adverse event may continue with either NIR178 or PDR001 as single agent, if the Investigator considers it to be in the patient's best interest to do so, following documented discussion with Novartis.

After a dose interruption, patients who are able to resume study treatment within the same treatment cycle (i.e. within 28 days of the last PDR001 dose) should resume dosing with NIR178 at the next scheduled dose within the same cycle. For AEs that resolve more than 28 days from the last dose of PDR001, both PDR001 and NIR178 must be restarted together with appropriate dose as soon as patient is able, and re-initiation of therapy must constitute the beginning of the next treatment cycle. Disease assessments will continue to occur at the frequency specified within the protocol (See [Section 7.2.1](#)), even if no longer in sync with cycle clock.

Non-immune related AEs (non-irAEs), resulting in dose delay of PDR001 or NIR178 lasting longer than 14 days will necessitate discontinuation of study drug. Exceptions may be made if the Investigator considers it to be in the patient's best interest to resume therapy, following documented discussion with Novartis. In the event of immune related AEs (irAEs) requiring treatment interruption, combination therapy with NIR178 and PDR001 can resume only when the specific irAE has resolved as outlined in [Table 6-2](#), patient requires no more than physiologic dose of steroids (steroid equivalent of ≤ 10 mg/day of prednisone), and patient has discontinued any other immunosuppressive drugs that were initiated for the irAE. Overall, for irAEs that do not recover to \leq Grade 1 or baseline at a dose of immunosuppression of ≤ 10 mg/day prednisone or equivalent within 12 weeks after initiation of immunosuppressive therapy, and/or requiring continuation of other immunosuppressive drugs, PDR001 and NIR178 must be permanently discontinued ([Figure 6-1](#)).

Figure 6-1 Management of toxicity requiring dose interruptions

[figure not shown]
[figure not shown]

[figure not shown]
Table 6-2 Criteria for dose reduction / interruption and re-initiation of NIR178 and PDR001 treatment for adverse drug reactions

The instructions provided in this table and the criteria for dose reduction / interruption are used to determine a protocol deviation.

[figure not shown]
Worst toxicity CTCAE^a grade	Recommended Dose Modification
Infusion reaction or hypersensitivity reaction	
Grade 1	Decrease infusion rate until recovery of the symptoms.
Grade 2	Stop infusion immediately, and keep line open. Follow institutional guidelines for the management and follow-up of infusion reaction. Restart infusion at 50% of previous rate under continuous observation. Ensure that there is a minimum observation period of 1 hour prior to restarting the infusion. If the AE recurs at the reinitiated slow rate of infusion, and despite oral pre-medication, then permanently discontinue study treatment.
Grade 3 and Grade 4	Discontinue infusion immediately, and discontinue study treatment. Provide supplemental oxygen, fluids, and other resuscitative measures as needed. Monitor vital signs (e.g. blood pressure, pulse, respiration, and temperature) every 15 ± 5 minutes until resolution.
Cytokine Release Syndrome (CRS)	
Grade 2	See instructions for Grade 2 Infusion Reaction above.
Grade 3 or Grade 4	Discontinue study treatment. Follow-up CRS as per institutional guidelines.
Ocular (uveitis, eye pain, blurred vision)	
Grade 1	Continue study treatment without dose modification. Ophthalmology consultation.
Grade 2	Hold study treatment. Urgent ophthalmology consultation. Upon resolution to ≤ Grade 1 may consider resuming study treatment without dose reduction after discussion with the Novartis Medical Monitor and in consultation with ophthalmology.
Grade 3 or Grade 4	Discontinue study treatment. Urgent ophthalmology consultation.

[figure not shown]
Worst toxicity CTCAE^a grade	Recommended Dose Modification
Pulmonary (pneumonitis)	
Grade 1	Consider study treatment hold. Manage per institutional practice, consultation with pulmonologist is recommended. Consider resuming study treatment upon radiographic evidence of improvement.
Grade 2	Hold study treatment. Pulmonary and infection workup, consultation with pulmonologist is recommended. Upon resolution to ≤ Grade 1, may resume study treatment without dose modification.
Grade 3 or Grade 4	Discontinue study treatment. Manage per institutional practice, consultation with pulmonologist is recommended.
<hr/>	
Cardiovascular	
ECG QTc-Interval prolonged; hypertension	
Grade 3	Hold study treatment. Upon resolution to Grade ≤ 1 or baseline (hypertension, QTc) or < 30 msec difference from baseline (QTc) within ≤ 7 days, may resume study treatment without dose modification after discussion with the Novartis Medical Monitor. Baseline ECG refers to the ECG(s) collected at screening.
Grade 4	Discontinue study treatment.
Other cardiovascular disorders	
Grade 2 (except myocarditis)	Hold study treatment. Upon resolution to Grade ≤ 1 or baseline, may resume study treatment without dose modification after discussion with the Novartis Medical Monitor.
Grade 2 myocarditis, or Grade ≥ 3 other cardiac disorders related to study treatment	Discontinue study treatment.

[figure not shown]
Worst toxicity CTCAE^a grade	Recommended Dose Modification
Gastrointestinal	
Diarrhea/colitis*	
Grade 1	May continue study treatment without dose modification. Manage per institutional standard guidelines which should include anti-diarrheal treatment, consideration of corticosteroid therapy, and hydration.
Grade 2	Hold study treatment. GI consultation. Upon resolution to ≤ Grade 1 and tapering of steroid requirement to ≤ 10 mg prednisone per day, resume study treatment without dose modification after discussion with the Novartis Medical Monitor.
Grade 3	Hold study treatment. GI consultation. Upon resolution to ≤ Grade 1 and tapering of steroid requirement to ≤ 10 mg prednisone per day, consider resuming study treatment after discussion with the Novartis Medical Monitor.
Grade 4	Discontinue study treatment.
AST and/or ALT elevation	
Grade 2 AST and/or ALT	Hold study treatment. Manage per institutional practice. Upon resolution to ≤ Grade 1 or baseline, consider resuming study treatment without dose modification. After resuming treatment with NIR178, close monitoring with at least weekly LFTs is recommended for 1 cycle of treatment. If suspicion of autoimmune hepatitis, the following confirmatory diagnostic serological markers are recommended: Serum autoantibodies including antinuclear (ANA), smooth muscle antibody (SMA) or antibody to liver-kidney microsomes (anti-LKM), Immunoglobulin levels, total globulins, and when possible liver biopsy.
Grade 3 AST and/or ALT ALT or AST >3 x ULN and TBL >2 x ULN (or international normalized ratio [INR] >1.5) ALT or AST >3 x ULN and symptoms of hepatitis (eg, fatigue, nausea, vomiting, right upper quadrant pain or tenderness, fever, rash, and/or eosinophilia [>5%])	Hold study treatment. Manage per institutional practices. Upon resolution to ≤ Grade 1 or baseline within 7 days, consider resuming PDR001 at the same dose and NIR178 at a lower dose after discussion with the Novartis Medical Monitor. After resuming treatment with NIR178, close monitoring with at least weekly LFTs is recommended for 1 cycle of treatment. Otherwise, discontinue study treatment. If suspicion of autoimmune hepatitis, the following confirmatory diagnostic serological markers are recommended: Serum autoantibodies including antinuclear (ANA), smooth muscle antibody (SMA) or antibody to liver-kidney microsomes (anti-LKM), Immunoglobulin levels, total globulins, and when possible liver biopsy.
Grade 4 AST and/or ALT	Discontinue study treatment.
Isolated total bilirubin elevation**	

[figure not shown]
Worst toxicity CTCAE ^a grade	Recommended Dose Modification
Grade 2	Hold study treatment. Upon resolution to ≤ Grade 1 or baseline, may continue study treatment without dose modification.
Grade 3	Hold study treatment. Upon resolution to ≤ Grade 1 or baseline, may consider resuming study treatment after discussion with the Novartis Medical Monitor.
Grade 4	See footnote**. Otherwise, discontinue study treatment.
Combined elevations of AST or ALT and total bilirubin	

For participants with normal baseline ALT and AST and total bilirubin value: AST or ALT >3.0 x ULN combined with total bilirubin >2.0 x ULN without evidence of cholestasis OR [AST or ALT >3x baseline OR > 8.0 xULN], whichever is lower, combined with [total bilirubin >2x baseline AND >2.0 x ULN]
	
Mandatory: Interrupt treatment and adjudicate for DILI: Repeat as soon as possible, preferably within 48 hours from awareness of the abnormal results, then with weekly monitoring of LFTs, or as clinically indicated, until AST, ALT, or total bilirubin have resolved ≤ ULN or to baseline. (Refer to the Section 6.2.2.1 for additional follow-up evaluations as applicable.) If causality assessment indicates that DILI is probable: Permanently discontinue participant from treatment. If not DILI: Treat the identified cause according to institutional guidelines. Once resolved, reduce by one dose level.

**Note: For participants with Gilbert's syndrome, at least 2-fold increase in direct bilirubin.
	
Asymptomatic amylase and/or lipase elevation***	
Grade 3 or Grade 4, not associated with symptoms or clinical manifestations of pancreatitis***	
Continue study treatment. If levels do not resolve to ≤ Grade 2 within ≤ 14 days after the initial report, hold study treatment. Upon resolution to ≤ Grade 2, may resume study treatment without dose modification, after discussion with the Novartis Medical Monitor.

Pancreatitis	
Grade 2/ radiologic evidence	
Hold study treatment. Manage per institutional practice. Upon resolution to ≤ Grade 1, may resume study treatment without dose modification, if no clinical evidence of pancreatitis and after discussion with the Novartis Medical Monitor.

[figure not shown]
Worst toxicity CTCAE^a grade	Recommended Dose Modification
Grade 3 or Grade 4	Discontinue study treatment.
Renal	
Serum creatinine	
Grade 2	Hold study treatment. Manage per institutional practice. Upon resolution to ≤ Grade 1, may resume study treatment without dose modification after discussion with the Novartis Medical Monitor.
Grade 3 or 4	Discontinue study treatment.
Musculoskeletal	
Grade 2 or Grade 3	Hold study treatment. Consider resuming study treatment without dose modification upon resolution to ≤ Grade 1 with appropriate management.
Grade 4	Discontinue study treatment. In some cases, resuming study treatment may be considered after discussion with the Novartis Medical Monitor and consultation with a rheumatologist.
Endocrine	
Hypothyroidism or hyperthyroidism	
Grade 2	May continue study treatment without dose modification. Management according to institutional practice.
Grade 3	Hold study treatment. Upon resolution to Grade ≤ 1 with appropriate management, may resume study treatment without dose modification. May resume therapy following resolution or control with physiologic hormone replacement.
Grade 4	
Other endocrine disorders	
Grade 2 and Grade 3	Hold study treatment. Upon resolution to Grade ≤ 1 with appropriate management, may resume study treatment without dose modification.
Grade 4	Hold study treatment. Grade 4 treatment-related endocrinopathies, such as adrenal insufficiency, adrenocorticotrophic hormone (ACTH) deficiency, hyper- or hypothyroidism, or glucose intolerance, which resolve or are adequately controlled with physiologic hormone replacement (corticosteroids, thyroid hormones) or glucose-controlling agents, respectively, may not require discontinuation after discussion with and approval from the Novartis Medical Monitor.
Neurology	

Worst toxicity CTCAE^a grade	Recommended Dose Modification
Grade 1	Consider study treatment hold, particularly for clinical suspicion of Guillain-Barre syndrome, encephalitis, aseptic meningitis, transverse myelitis, or peripheral neuropathy.
Grade 2	Hold study treatment. In some cases, resuming study treatment may be considered after discussion with the Novartis Medical Monitor.
Grade 3 or Grade 4	Discontinue study treatment.
Dermatology (rash)	
Grade 1	Continue study treatment without dose modification. Topical steroids, antihistamines, topical emollients
Grade 2	Consider holding study treatment. Topical or oral steroids, antihistamines. If study treatment is held and resolution to \leq Grade 1, resume study treatment without dose modification.
Grade 3 or Grade 4	Hold study treatment. Manage per institutional practice. After resolution to \leq Grade 1, consider resuming study treatment after discussion with the Novartis Medical Monitor.
